10.7 Quality Assurance Audit

A Sponsor representative or designee may request access to all clinical investigation records, including source documentation, for inspection during a Quality Assurance audit.

In the event that an Investigator is contacted by a Regulatory Agency in relation to this clinical investigation, the Investigator will notify Sponsor immediately. The Investigator and Research Coordinator must be available to respond to reasonable requests and audit queries made during the audit process. The Investigator must provide Sponsor with copies of all correspondence that may affect the review of the current clinical investigation (e.g., Form FDA 483, Inspectional Observations, Warning Letters, Inspection Reports, etc.). Sponsor may provide any needed assistance in responding to regulatory audits.

10.8 Committees

10.8.1 Steering Committee

The Steering Committee is assigned by the Sponsor and consists of investigators. The Sponsor will also be represented on the committee. Meeting minutes from this committee will be filed with the sponsor.

The Steering Committee is responsible for overseeing the scientific and operational aspects of the clinical investigation. This committee will meet regularly to monitor subject enrollment, general data collection and non-compliance with the CIP at individual centers, to review operational issues that may

arise and warrant a CIP amendment or other corrective action, and to determine policy regarding any publications arising from data generated from the performance of the clinical investigation.

10.8.2 Clinical Events Committee (CEC)

The Clinical Events Committee (CEC) is an independent adjudication body comprised of qualified physicians who are not participants in the clinical investigation. The CEC will review and adjudicate prespecified events reported by Investigators or identified by Safety personnel for the clinical investigation as defined in the CEC charter and according to definitions provided in this CIP.

11.0 DATA HANDLING AND RECORD KEEPING

Sponsor and/or its affiliates will maintain documentation of the systems and procedures used in data collection for the duration of the clinical investigation.

CRF data collection will be performed through a secure web portal and only authorized personnel will access the Electronic Data Capture (EDC) system using a unique username and password to enter, review, or correct data. Passwords and electronic signatures will be strictly confidential.

The data will be subjected to consistency and validation checks within the EDC system and supplemental review by the Sponsor.

At the conclusion of the clinical investigation, completed CRF images with the date-and-time stamped electronic audit trail indicating the user, the data entered, and any reason for change (if applicable) will be provided to the investigational sites.

For the duration of the clinical investigation, the Investigator will maintain complete and accurate documentation including, but not limited to, medical records, clinical investigation progress records, laboratory reports, CRFs, signed ICFs, device accountability records (if applicable), correspondence with the IRB/EC and clinical investigation monitor/Sponsor, adverse event reports, and information regarding subject discontinuation or completion of the clinical investigation.

11.1 Protection of Personally Identifiable Information

The Sponsor respects and protects personally identifiable information collected or maintained for this clinical investigation.

The Sponsor implements technical and physical access controls to ensure that Personal Information is accessible only to, and processed only on, a 'need to know' basis, including periodic review of access rights, and revocation of access when an individual's employment is terminated or the individual transitions to a role that does not require access to Personal Information, and appropriate restrictions on physical access to premises, facilities, equipment, and records containing Personal Information.

The Sponsor requires the investigational sites to transfer into Sponsor's data management systems only pseudonymous Personal Information (key-coded) necessary to conduct the Clinical Investigation, such as the patient's medical condition, treatment, dates of treatment, etc. The Sponsor discloses as part of the clinical investigation informed consent process that some Sponsor representatives still may see Personal Information at the participating sites for technical support of the participating physicians on the device implant or procedures, monitoring and quality control purposes. Confidentiality of Personal Information will be observed by all parties involved at all times throughout the clinical investigation. The

privacy of each subject and confidentiality of his/her information will be preserved in reports and when publishing any data.

The Sponsor data management systems and processes were designed, developed, and tested according to industry standards to appropriately safeguard Confidential Information (including any Personal Information) against unauthorized access and/or interference by third parties, intrusion, theft, destruction, loss or alteration. Clinical Investigation data are encrypted in transit and at rest.

The Sponsor maintains a Privacy Incident procedure that complies in all respects with Applicable Law and industry best practices.

11.2 Data Management Plan

A Data Management Plan (DMP) will describe procedures used for data review, data cleaning, and issuing and resolving data discrepancies. If appropriate, the DMP may be updated throughout the duration of the clinical investigation. All revisions will be tracked and document controlled.

11.3 Source Documentation

Regulations and GCP require the Investigator to maintain information in the subject's original medical records that corroborates data collected on the CRFs. In order to comply with these regulatory requirements/GCP, the following information should be included in the subject record at a minimum and if applicable to the clinical investigation:

- Medical history/physical condition of the subject before involvement in the clinical investigation sufficient to verify CIP entry criteria
- Dated and signed notes on the day of entry into the clinical investigation referencing the Sponsor, CIP number, subject ID number and a statement that informed consent was obtained
- Dated and signed notes from each subject visit (for specific results of procedures and exams)
- Adverse events reported and their resolution, including supporting documents, such as discharge summaries, catheterization laboratory reports, ECGs, and lab results including documentation of site awareness of SAEs and of Investigator assessment of device relationship for SAEs
- Notes regarding CIP-required and prescription medications taken during the clinical investigation (including start and stop dates)
- Subject's condition upon completion of, or withdrawal from, the clinical investigation
- Any other data required to substantiate data entered into the CRF
- Patient reported outcome measures may be completed using CRF worksheets. These serve as the source documentation.
- Patient reported outcome measures may be completed using electronic sources, such as directly into an Investigator's electronic health record. In this event, the direct entry by the subject is considered the source.

11.4 Case Report Form Completion

Primary data collection based on source-documented hospital and/or clinic chart reviews will be performed clearly and accurately by site personnel trained on the CIP and CRF completion. The

Investigator will ensure accuracy, completeness, legibility and timeliness of the data reported to the Sponsor on the CRFs and in all required reports.

Data on CRFs will be collected for all subjects that are enrolled into the clinical investigation.

Only authorized site personnel will be permitted to enter the CRF data through the EDC system deployed by the Sponsor. An electronic audit trail will be used to track any subsequent changes of the entered data.

11.5 Record Retention

The Sponsor and Investigator/Site will archive and retain all documents pertaining to the clinical investigation as per the applicable regulatory record retention requirements. The Investigator must obtain permission from Sponsor in writing before destroying or transferring control of any clinical investigation records.

12.0 ETHICAL CONSIDERATION

12.1 Institutional Review Board/Medical Ethics Committee Review and Approval

Institutional Review Board (IRB)/ Ethics Committee (EC) approval for the CIP and ICF/other written information provided to the patient will be obtained by the Principal Investigator at each investigational site prior to consenting and enrolling patients in this clinical investigation. The approval letter must be received prior to the start of this clinical investigation and a copy must be provided to the Sponsor.

Any amendments to the CIP as well as associated ICF changes will be submitted to the IRB/EC and written approval obtained prior to implementation according to each institution's IRB/EC requirements.

No changes will be made to the CIP or ICF or other written information provided to the patient without appropriate approvals, including IRB/EC, the Sponsor, and the regulatory agencies (if applicable).

Until the clinical investigation is completed, the Investigator will advise his/her IRB/EC of the progress of this clinical investigation, per IRB/EC requirements. Written approval must be obtained from the IRB/EC yearly to continue the clinical investigation, or according to each institution's IRB/EC requirements.

No investigative procedures other than those defined in this CIP will be undertaken on the enrolled subjects without the written agreement of the IRB/EC and the Sponsor.

13.0 CLINICAL INVESTIGATION CONCLUSION

The clinical investigation will be concluded when:

- All sites are closed AND
- The final report has been provided to Investigators or the Sponsor has provided formal documentation of clinical investigation closure.

14.0 PUBLICATION POLICY

The data and results from the clinical investigation are the sole property of the Sponsor. The Sponsor shall have the right to access and use all data and results generated during the clinical investigation. The Investigators will not use this clinical investigation-related data without the written consent of the Sponsor for any purpose other than for clinical investigation completion or for generation of publication materials, as referenced in the Clinical Trial Agreement. Single-center results are not allowed to be published or presented before the multi-center results. Any proposals for publications or presentations by the Investigators must be reviewed and approved by the Sponsor in a timely manner to enable Sponsor review in compliance with the Sponsor's publication policy set forth in the Clinical Trial Agreement.

The Sponsor will be responsible for determining whether to register the clinical investigation on www.clinicaltrials.gov or any other clinical trials, in accordance with the International Committee of Medical Journal Editors guidelines, or any other applicable guidelines. In the event Sponsor determines that the clinical investigation should be registered, Sponsor shall be responsible for any such registration and results posting as required by the ClinicalTrials.gov website. Institution and/or Principal Investigator(s) shall not take any action to register the clinical investigation.

15.0 RISK ANALYSIS

15.1 Anticipated Clinical Benefits

The information collected in this study will be added to the current knowledge and understanding of treatment options for patients with SCS systems that do not currently provide sufficient pain relief.

15.2 Foreseeable Adverse Events and Anticipated Adverse Device Effects

Risks associated with the specified devices and procedure are described in the relevant IFU. There may be risks related to the study devices that are unknown at present. Likewise, the exact frequency of the risk may be unknown.

15.3 Residual Risks Associated with the Study Devices, as Identified in the Risk Analysis Report

The clinical risks associated with neurostimulation systems are well known. Any potential residual risks are considered outweighed by the benefits, and the overall residual risk was determined to be acceptable. Clinical evidence demonstrates acceptable safety and performance of the device under this post-market study.

15.4 Risks Associated with Participation in this Clinical Investigation

The risks involved with this study are comparable to those associated with the implant of any other commercially available neurostimulation system. Risks specific to each device are outlined in the associated IFU, and these disclosed risks are not modified by participation in this trial.

15.5 Steps Taken to Control or Mitigate Risks

[figure not shown]
The devices used in this study are approved and in commercially distribution. Risks associated with the use of the device under investigation are minimized through device design, Investigator selection and training, pre-specified patient eligibility requirements, and study monitoring to ensure adherence to the

protocol and the use of a DMC. All adverse events and device deficiencies will be reported to the Sponsor and will be monitored internally for safety surveillance purposes.

15.6 Risk to Benefit Rationale

Any undesirable side effects, under normal conditions of use, are considered acceptable risks when weighed against the performance of the device and benefits to the subject.

APPENDIX I: ABBREVIATIONS AND ACRONYMS

AE	Adverse Event
CEC	Clinical Events Committee
CIP	Clinical Investigation Plan
CRF	Case Report Form
CRPS	Complex Regional Pain Syndrome
DMP	Data Management Plan
DRG	Dorsal Root Ganglion
EC	Ethics Committee
EDC	Electronic Data Capture
FAS	Full Analysis Set
GCP	Good Clinical Practice
HIPPA	Health Insurance Portability and Accountability Act
ICF	Informed Consent Form
IFU	Instructions for Use
IPG	Implantable Pulse Generator
IRB	Institutional Review Board
MRI	Magnetic Resonance Imaging
NRS	Numerical Rating Scale
PCS	Pain Catastrophizing Scale
PRO	Patient Reported Outcome
PVAQ	Pain Vigilance and Awareness Questionnaire
RCT	Randomized Controlled Trial
SAE	Serious Adverse Event
SCS	Spinal Cord Stimulation
UADE	Unanticipated Adverse Device Effect

Clinical Investigation Plan APPENDIX II: SITE CONTACT INFORMATION

ABT-CIP-10460 Ver. A Study Name: PROLONG (CRD_960)

Clinical Investigation Plan APPENDIX III: CASE REPORT FORMS

Clinical Investigation Plan APPENDIX IV: INFORMED CONSENT FORM

ABT-CIP-10460 Ver. A Study Name: PROLONG (CRD_960)

Clinical Investigation Plan APPENDIX V: MONITORING PLAN

APPENDIX VI: REVISION HISTORY

This CIP may be amended as appropriate by the Sponsor. Rationale will be included with each amended version in the revision history table below. The version number and date of amendments will be documented.

IRB/EC and relevant Regulatory Authorities, if applicable, will be notified of amendments to the CIP.

Amendment Number	Version	Date	Details	Rationale
Not Applicable	А	23 JAN 2019	First release of CIP	NA

APPENDIX VII: CIP SUMMARY

Clinical Investigation Name and Number	CRD_960 Prolong		
Objectives	The objectives of this study are to evaluate the effectiveness of Abbott neurostimulation devices in restoring pain relief, improving quality of life, and reducing related medication use for patients with failed SCS.		
Study Devices	Any market-released Abbott BurstDR-capable or DRG neurostimulation device may be used in this study along with its relevant accessories. This study allows for the inclusion of future iterations of Abbott's neurostimulation systems and expanded indications as they receive approval from the applicable country regulatory authority.		
Number of Subjects Required for Inclusion in Clinical Investigation	100 subjects will be registered at up to 40 sites in the US		
Clinical Investigation Design	Prospective, multi-center, open-label, post-market		
Endpoints	 NRS Patient reported pain relief Patient satisfaction Physician satisfaction PROMIS-29 Pain Catastrophizing Scale (PCS) Pain Vigilance and Awareness Questionnaire (PVAQ) Pain condition-related medication usage 		
Subject Follow-up	 Enrollment Baseline Start of Trial (if applicable) End of Trial (if applicable) Permanent Implementation 3-month follow-up 6-month follow-up 12-month follow-up 18-month follow-up 24-month follow-up 		
Inclusion Criteria	 Patient must provide written informed consent prior to any clinical investigation related procedure. 		

	2. Patient has a spinal cord stimulator implanted for chronic, intractable
	pain.
	3. Patient has inadequate pain relief from their current SCS system.
	 Patient has a pain NRS ≥ 6.
	5. Physician has determined that the patient's original pain is still addressable with neurostimulation.
Exclusion Criteria	 Patient is enrolled, or intends to participate, in a competing clinical study, as determined by Abbott.
	Patient is seeking care for a new pain complaint outside of the original indication for SCS.
	 Presence of other anatomic or comorbid conditions, or other medical, social, or psychological conditions that, in the Investigator's opinion, could limit the patient's ability to participate in the clinical investigation or to comply with follow-up requirements.
	 Physician has determined that patient's pain relief is inadequate due to a malfunction or damage to the existing system.
	5. Patient requires frequent MRI.
	Patient is involved in active disability litigation related to their pain or seeking worker's compensation.
	7. Patient is a member of a vulnerable population (See Section 5.2.2.1).

1.0 SYNOPSIS OF STUDY DESIGN

1.1 Purpose of the Statistical Analysis Plan

This statistical analysis plan (SAP) is intended to provide a detailed and comprehensive description of the planned methodology and analysis to be used for PROLONG (CRD_960) clinical investigation. This plan is based on the ABT-CIP-10277 Ver. A, January 23, 2019 Clinical Investigation Plan (CIP).

1.2 Clinical Investigation Objectives

The objectives of this study are to evaluate the effectiveness of Abbott neurostimulation devices in restoring pain relief, improving quality of life, and reducing related medication use for patients with failed SCS.

1.3 Clinical Investigation Design

This study is a prospective, multi-center, open-label, post-market study designed to evaluate the effectiveness of Abbott neurostimulation devices in restoring pain relief for patients who no longer receive adequate therapeutic benefit from SCS. The Investigator will select the most appropriate BurstDR or DRG implementation method according to their standard of care.

A trial of BurstDR or DRG may be performed as deemed appropriate by the Investigator. This includes the option for multiple trials to test both BurstDR and DRG therapy. Similarly, the permanent implementation method will be performed as deemed appropriate by the Investigator.

This clinical investigation will enroll up to 100 patients at up to 40 sites in the US. subjects will be followed for 24 months after permanent

implementation.

1.4 Endpoints

The clinical investigation has the following end points which will be assessed and reported for all protocol defined visits:

- Numerical rating scale (NRS) for pain intensity
- Patient reported pain relief
- Patient satisfaction
- Physician satisfaction
- PROMIS-29
- Pain Catastrophizing Scale (PCS)
- Pain Vigilance and Awareness Questionnaire (PVAQ)
- Pain condition-related medication usage

1.5 Randomization

Not applicable.

1.6 Blinding

2.0 ANALYSIS CONSIDERATIONS

2.1 Analysis Populations

2.1.1 Full Analysis Set (FAS)

2.2 Statistical Methods

Descriptive analysis will be performed to summarize baseline, clinical, effectiveness and safety event data. Depending on the type of data (e.g., continuous or categorical), statistical methods described in the following sections will be used.

2.2.1 Descriptive Statistics for Continuous Variables

For continuous variables (e.g., age, etc.), results will be summarized with the numbers of observations, means, and standard deviations, with quartiles, minimums, maximums, and 95% confidence intervals for the means as per the table mockups.

2.2.2 Descriptive Statistics for Categorical Variables

For categorical variables (e.g. gender, etc.), results will be summarized with subject counts and percentages/rates, etc. Two-sided exact 95% Clopper-Pearson confidence intervals may be presented as appropriate.

2.3 Endpoint Analysis

2.3.1 Endpoints

[figure not shown]
The following endpoints will be successively evaluated in the order shown below at 0.05 significance level.

- 1. Change in NRS score for all subjects
- 2. Change in PCS Total score for all subjects
- 3. Change in NRS score for SCS therapy subjects
- 4. Change in NRS score for DRG therapy subjects
- 5. Change in Promis-29 Pain Interference T-score for all subjects
- 6. Change in Promis-29 Physical Function T-score for all subjects

Change is defined as change in score from baseline to 6 months and is calculated as:

Change in score = Score at Baseline - Score at 6-month

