2.0 CLINICAL STUDY OVERVIEW

2.1 Clinical Study Objectives

The objectives of this study are to evaluate the effectiveness of Abbott neurostimulation devices in restoring pain relief, improving quality of life, and reducing related medication use for patients with failed SCS.

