3.0 CLINICAL INVESTIGATION DESIGN

This study is a prospective, multi-center, open-label, post-market study designed to evaluate the effectiveness of Abbott neurostimulation devices in restoring pain relief for patients who no longer receive adequate therapeutic benefit from SCS. The Investigator will select the most appropriate BurstDR or DRG implementation method according to their standard of care.

A trial of BurstDR or DRG may be performed as deemed appropriate by the Investigator. This includes the option for multiple trials to test both BurstDR and DRG therapy. Similarly, the permanent implementation method will be performed as deemed appropriate by the Investigator.

This clinical investigation will enroll up to 100 patients at up to 40 sites in the US. Subject enrollment is expected to be completed within 12 months; subjects will be followed for 24 months after permanent implementation.

The clinical investigation has been designed to involve as little pain, discomfort, fear, and any other foreseeable risk as possible for subjects. Refer to the Risks Analysis section of this investigation plan for details.

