6.3 Permanent System Implementation

Permanent implementation of the chosen neurostimulation system will be performed according to the Investigator's standard operating procedures. The stimulator will be activated and programmed by trained personnel and/or an Abbott representative either during post-operative recovery or at an office visit in accordance with standard operating procedures. The subject's stimulator will be programmed according to the most recent Abbott programming guidance. After programming, the subject will receive a patient controller and will be instructed on how to use the system to relieve their pain. Subjects will be able to adjust the stimulation to ensure the best results.

The following data will be recorded during permanent implementation:

- Neurostimulation system details
- Device programming
- Device-related adverse events (if applicable)

- Serious adverse events (if applicable)
- Device deficiency (if applicable)
- Withdrawal (if applicable)
- Death (if applicable)

Neither the physician nor the subject should actively attempt to wean opioid usage for the first 45 days after permanent implementation. After this period, Investigators are encouraged to decrease opioid usage according to current guidelines or practices.

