8.2 Statistical Analyses

Summary statistics will be provided and significance values will be provided for comparisons and measures of change. Validated questionnaires will be assessed per their respective instructions.

- 8.3 Sample Size Calculation and Assumptions
- 8.4 Timing of Analysis
- 8.5 Subgroup Analysis
- 8.6 **Procedures for Accounting for Missing Data**
- 8.7 Planned Interim Analysis
- 8.8 Statistical Criteria for Termination

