2.3.2 Descriptive Endpoints

In addition to the above endpoints, data from additional descriptive endpoints or timepoints will be summarized. All analyses will be based on subjects in the Full Analysis Set.

- For NRS, descriptive statistics as defined in section 2.2.1 will be provided at baseline and all scheduled post-baseline visits. Absolute change from baseline summary will also be provided at each scheduled post-baseline visit.
- For Patient reported pain relief, percent change in NRS score from baseline to each scheduled post-baseline visit summary will be provided as defined in section 2.2.1.
- For PROMIS-29, PCS and PVAQ questionnaire data, descriptive statistics as defined in section 2.2.1 will be provided at baseline and all scheduled postbaseline visits. Change from baseline summary will also be provided for each scheduled post baseline visit. All the questionnaire data will be scored according to the scoring manuals prior to data analysis. The weblinks to the scoring manuals are provided in the reference section.
- For Patient and Physician Satisfaction, descriptive statistics as defined in section 2.2.2 will be provided for each satisfaction category.
- For all Pain condition related medications, descriptive statistics as defined in section 2.2.2 will be provided for in Full Analysis Set
 - Subjects who took pain medication at baseline and stopped post-baseline
 - Subjects who did not take pain medication at baseline but started post-baseline
 - o Subjects who increased dose from baseline to each post-baseline visit
 - o Subjects who decreased dose from baseline to each post-baseline visit

For pain condition related medication usage, the total morphine milligram equivalent (MME) dosage will also be calculated for each patient. The weblink for MME calculation is provided in the reference section of this SAP. Descriptive statistics as described in section 2.2.1 will be provided for total MME.

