2.7 Study/Trial Success

2.8 Subgroups for Analysis

Subgroup analysis using variables such as therapy (DRG vs SCS), salvage method and manufacturer type may be performed as needed for exploratory purposes.

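### Should the DRG-only pain test stand ahead of the two all-subject PROMIS-29 tests in the SAP 2.3.1 sequence?

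*SAP*

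**What the plan says.** SAP 2.3.1 introduces its list with "The following endpoints will be successively evaluated in the order shown below at 0.05 significance level". The order is:

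1. NRS, all subjects
2. PCS total, all subjects
3. NRS, SCS therapy subjects
4. NRS, DRG therapy subjects ("Change in NRS score for DRG therapy subjects")
5. PROMIS-29 Pain Interference, all subjects
6. PROMIS-29 Physical Function, all subjects

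All six are changes from baseline to 6 months. SAP 4.1 records that this testing was added to what the protocol specified, by decision of the study team.

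SAP 2.8 says: "Subgroup analysis using variables such as therapy (DRG vs SCS), salvage method and manufacturer type may be performed as needed for exploratory purposes".

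The protocol's objectives (2.1) are "restoring pain relief, improving quality of life, and reducing related medication use". Therapy is not assigned by the design; Protocol 3.0 says: "The Investigator will select the most appropriate BurstDR or DRG implementation method according to their standard of care". No visible text sets a number of DRG subjects.

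The headings where a stopping rule, a sample-size basis or a subgroup plan would sit (SAP 2.4, 2.7 and 2.10; Protocol 8.3 and 8.5) carry no text in the public copies, and a figure just above the testing sentence in SAP 2.3.1 is not shown. None of this can be counted as absent from the plan.

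**The concern.** An ordered list with each test at the full 0.05 reads most naturally as a fixed-sequence procedure, in which testing stops at the first non-significant result. On that reading a subgroup of unknown size stands in front of two whole-population tests. Those two are the only places where PROMIS-29, the study's quality-of-life instrument, enters the ordered list. If few investigators chose DRG, step 4 could fail for lack of numbers, or not be estimable at all, and the formal PROMIS-29 conclusions would be lost for a reason unrelated to PROMIS-29.

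SAP 2.8 seems to sharpen the point. It names therapy among the variables for optional, exploratory analysis, while 2.3.1 gives two therapy-specific results a formal place in the sequence.

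**Working it through.** **No stated figure to reproduce.** The visible text gives no effect size, standard deviation, power or DRG share. The planned total of 100 (Protocol 5.7) and the order and level of the tests (SAP 2.3.1) come from the documents. Every other input below is an assumption.

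**Step 4 alone.** For a two-sided paired test on n subjects with standardized change d, power is the probability that a noncentral t variable, with n − 1 degrees of freedom and noncentrality d√n, exceeds the 0.975 point of the central t. The smallest n reaching 80% power is:

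| NRS d | DRG subjects needed | Power at that n |
|---|---|---|
| 0.5 | 34 | 0.808 |
| 0.8 | 15 | 0.821 |
| 1.0 | 10 | 0.803 |

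**Chance that step 4 cannot be computed.** With 85 evaluable subjects and a 5% DRG share, the probability of fewer than two DRG subjects is 0.95^85 + 85 × 0.05 × 0.95^84 = 0.0128 + 0.0572 = 0.070.

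**Whole sequence.** The simulation used 85 subjects with DRG membership drawn at random at the given share, correlation 0.5 between outcomes, PCS d = 0.5, and the same NRS d in both therapies. Success counts only in the favourable direction. Testing stops at the first p of 0.05 or more, or at a subgroup with fewer than two subjects. The table shows formal success on Pain Interference under the current order, then with only the DRG test moved last:

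| NRS d | PROMIS-29 d | 10% DRG | 20% DRG | 30% DRG |
|---|---|---|---|---|
| 0.5 | 0.4 | 23 → 94% | 46 → 94% | 63 → 92% |
| 0.8 | 0.3 | 41 → 78% | 68 → 78% | 76 → 78% |
| 0.8 | 0.4 | 49 → 95% | 82 → 95% | 92 → 95% |
| 1.0 | 0.4 | 65 → 95% | 91 → 95% | 95 → 95% |
| 1.5 | 0.4 | 86 → 95% | 95 → 95% | not run |
| 2.0 | 0.4 | 92 → 95% | not run | not run |

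The cost is large when a small DRG group meets a moderate NRS change, and it fades as either grows. Nothing in the documents says DRG will be the smaller group. If it were the larger, the SCS test at step 3 would be the tighter gate.

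**Price of moving the DRG test.** Formal DRG success would then depend on both PROMIS-29 tests. At NRS d = 0.8, current order then DRG last:

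| PROMIS-29 d | 10% DRG | 20% DRG | 30% DRG |
|---|---|---|---|
| 0.5 | 51 → 50% | 85 → 84% | 96 → 95% |
| 0.4 | 51 → 48% | 85 → 79% | 96 → 89% |
| 0.3 | 51 → 35% | 85 → 58% | 96 → 64% |

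At a 30% share and PROMIS-29 d = 0.3, Pain Interference gains 78 − 76 = 2 points and DRG loses 96 − 64 = 32. Under either order the familywise error is 0.05, and the chance that all six tests succeed is the same.

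**SAP 2.3.1 beside SAP 2.8.** The first names two within-therapy changes as numbered, tested endpoints. SAP 2.3.2 then opens a separate descriptive tier for data beyond those endpoints. Section 2.8 concerns analyses that may or may not be done, and its example is a contrast between therapies. The two sections can be read together without conflict: steps 3 and 4 are tested, and any further subgroup work is exploratory.

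**What a blocked step 5 would lose.** SAP 2.3.2 covers PROMIS-29 regardless: "Change from baseline summary will also be provided for each scheduled post baseline visit", in the format of SAP 2.2.1, which includes 95% confidence intervals for means. Protocol 8.2 adds that "significance values will be provided for comparisons and measures of change". The estimate, its interval and a nominal p-value would all be available; only the formal label would go.

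**The case for a change.** The best argument for acting is that the query is cheap and the possible loss is not small. A few sentences would say whether testing stops at the first failure, what happens if step 4 cannot be estimated, and that the order is deliberate. If the list were not a stopping sequence, six independent tests at 0.05 would carry a familywise error of 1 − 0.95^6 = 0.265 (illustrative, since these endpoints are correlated), so the stop rule matters either way. Because "Neurostimulation system details" are recorded at permanent implementation, DRG counts could guide the order without anyone looking at outcomes.

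Part of this stands. The visible text leaves the stop rule to inference, and with fewer than about 15 DRG subjects and an NRS change of 0.8 or less, step 4 would decide most of what happens at steps 5 and 6. But the rule may already be in SAP 2.10, and writing it down would alter no analysis that an analyst reading the list as a fixed sequence would run. A step that cannot be computed cannot be declared significant, so the sequence would end there. Confirming the order asks the sponsor to repeat what the SAP already states. Reordering by accrued DRG counts would reopen a pre-specified sequence in an open-label study for a gain that depends on unknown effect sizes.

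**Conclusion.** No change to the plan follows. The order is as described, and if testing stops at the first failure, the DRG-only test, like the SCS-only test before it, precedes both PROMIS-29 tests. The effect on formal Pain Interference success in the settings tabulated above runs from nothing (30% DRG share, NRS d = 1.0, PROMIS-29 d = 0.4) to about 71 points (10% share, NRS d = 0.5, PROMIS-29 d = 0.4: 94 − 23). Where it falls in that range depends on the stop rule, the DRG share and the effect sizes, none of which the visible text gives.

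The sequence is a fair trade-off. Restoring pain relief is the first stated objective and the only one named in the design statement, so putting pain within each therapy ahead of PROMIS-29 is reasonable. Any pre-specified order controls the familywise error, and the alternative takes power from the DRG conclusion. SAP 2.8 does not contradict the list. PROMIS-29 change is reported with intervals whatever happens at step 4. At most, the sponsor could be asked, at low priority, whether SAP 2.10 already covers the stop rule and a step 4 that cannot be estimated.
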